#### 7.2 Randomization Method

Randomization will be carried out using SAS® (SAS Institute Inc., USA) version 9.4 or higher.

Confidential Page 44 of 91

Randomization will be done in blocks using PROC PLAN such that the design is balanced. The order of receiving reference and test formulations for each patient during two-periods of study will be determined according to the randomization schedule for Stage 1 and Stage 2 (as applicable). Randomization will be generated separately for each stage.

	Period 1	Period 2
Sequence 1	Test (T)	Reference (R)
Sequence 2	Reference (R)	Test (T)

# Screening and Randomization Numbering

Each patient will be assigned a unique number that will serve to identify laboratory specimens and all documents and will be used throughout the study. If a patient fails to qualify for allocation to the study i.e. is a screen failure, his/her number must not be reused for another patient.

The screening number will be a combination of the center number, the project number and the patient number. The center number will be assigned by to the investigative site (e.g., A, B, C, D) and subsequent sites are assigned consecutive alphabet numbers. Upon signing the informed consent form, the patient will be assigned a screening number by the Investigator. At each site, the first patient consented is assigned screening number e.g., and subsequent patients are assigned consecutive numbers (e.g., the second patient consented is assigned screening number to the third patient is assigned screening number of the third patient is assigned to a patient, that number will not be reused for any other patient.

If the patient is deemed eligible for enrollment into the study and will commence dosing with IMP in Period 1, then a randomization number will be assigned. The randomization number will be assigned by a combination of Site ID and Dosing sequence (e.g., A-01 where A is Site ID and 01 is number of first patient dosed, A-02 where A is site ID and 02 is number of second patient dosed). Patient will be randomized on first come first serve basis and will be given a randomization number accordingly irrespective of their screening number.

There should be a source document maintained at the site which links the screening number to the randomization assignment number (once assigned) and this information will also be reflected in screening and enrollment log of site investigator file.

Confidential Page 45 of 91

#### 7.3 Blinding

This is an open label study. However, the bio-analyst at will be blinded to the randomization sequence of study drug administration to each of the patient. Samples that are shipped to the analytical laboratory will not contain treatment information on the sample label.

## 7.4 Duration of Study

Total expected study duration will be approximately 64 days consisting of:

- · Screening period including 10-day Dose Stabilization period: 40 days
- Treatment Period: 16 days
- End of Study: on Day 16
- Safety follow-up visit: On Day 24 ± 2 days; 8 ± 2 days after End of Study

For patients who are already receiving a stable dose of Lynparza® (olaparib) tablets (2\*150 mg twice daily) for at least 10 days before screening visit, the duration of screening period will be 30 days. Expected study duration will be approximately 54 days.

#### 7.5 Washout

There will be no Washout period between study periods.

# 7.6 Premature Termination of the Study

The sponsor reserves the right to discontinue the participation of either an individual site or the whole study at any time, for any reason, including, but not limited to the following:

- Determination of unexpected, significant, or unacceptable risk to participants;
- Patient enrolment is unsatisfactory;
- The Investigator has received from the sponsor all investigational medicinal products, means and
  information necessary to perform the clinical study and has not included any patient after a reasonable
  period of time mutually agreed upon;
- Non-compliance of the investigator, delegated staff with any provision of the clinical study protocol, and/or breach of the applicable laws and regulations or breach of the ICH GCP.

The investigator or the CRO reserves the right to discontinue the study for safety reasons at any time. The Ethics Committee (EC) or Regulatory Authority may ask to terminate the study, if there are major violations of ethical considerations or due to any serious adverse event(s). In all cases sponsor needs to be notified prior to study termination. Reasons for termination of study will be provided to patients. In case sponsor/PI

Confidential Page 46 of 91

decides to terminate the study, the reason(s) for the termination will be notified to the EC and/or Regulatory Authority as applicable within 30 working days.

In the case that the study is discontinued prematurely for any reason including lack of commercial interest in pursuing the new drug application, a summary report will be submitted within 3 months. The summary report should provide a brief description of the study, the number of patients exposed to the drug, dose and duration of exposure, details of adverse drug reactions, if any, and the reason(s) for discontinuation of the study.

#### 8.0 INVESTIGATIONAL MEDICINAL PRODUCTS

Test Product (T)	: Olaparib tablets, 150 mg
Reference Product (R)	: Lynparza® (olaparib) tablets 150 mg  Manufactured for:

# 8.1 Procurement, Storage and Accountability Procedures for Investigational Medicinal Products

## 8.1.1 Receipt and storage of Investigational Medicinal Products

Adequate supplies of investigational medicinal products (IMPs) for dose administration and sample retention purpose will be received by Pharmacy custodian at clinical facility of sponsor. Test and reference products will be received in their respective pack as supplied by sponsor or as per the storage container / label information provided. After receipt of IMPs, they will be transferred to the pharmacy. IMPs will be stored in a secure area with restricted access, under controlled storage conditions described in the product package labelling, unless otherwise instructed per protocol or IMP management plan. Certificates of analysis (COA) with the details of the product will be received from sponsor.

IMPs sufficient for dosing and retention shall be distributed to sites by

IMPs shall be distributed to sites in containers labeled with the details of Product name, Product Type (Test/Reference), Strength, No. of dosage units, Manufacturer, Batch or Lot No., Expiry date and Storage conditions. IMP management plan will be prepared to describe the IMP handling, storage, distribution/dispensing in detail.

The Investigator has overall responsibility for ensuring that IMPs are stored in a safe, limited access location, according to the conditions noted on the label. All IMPs are to be stored at 20°C to 25°C (68°F to 77°F), excursions permitted to 15°C to 30°C (59°F to 86°F), unless otherwise specified in the label. In case of temperature excursion (storage outside the labeled storage conditions) of IMP, the monitor must be contacted without delay. And in such case the investigator will be instructed by the consultation with sponsor) to either go ahead with the use of IMP or quarantine the IMP.

# 8.1.2 Accountability of Investigational Medicinal Products

Confidential Page 47 of 91

Accountability for each unit of the IMPs will be documented in the respective logs at individual investigator sites. The inventory log of IMP shipments will be maintained at

and at the

## 8.2 Dispensing

Dispensing will be done by the delegated site personnel for the IMPs received from

Only the Investigator and his/ her team will be responsible for the dispensing/administration/dosing of

IMPs at the sites. Only patients randomized in the study will receive IMPs. The IMPs will be issued to the
patient(s) according to the randomization schedule. Treatments for individual patients will be dispensed at
the study sites. Patient will be given adequate IMPs for dosing at home for Days 2 to 4 (morning and
evening), Day 5 (morning), Days 10 to 12 (for morning and evening) and Day 13 (morning). Patients will be
reminded to store the IMPs in the original package at 20°C to 25°C (68°F to 77°F) and to return all unused
IMPs to the study staff.

The Investigator team will be responsible for the accountability of administered/dosed IMPs at the study site. The drug accountability log for recording the receipt, issuance to the patients, and return of the IMPs will be maintained by the Investigator or authorized personnel. Limited responsibility may be delegated to a pharmacy representative if the investigator chooses to use a hospital or clinical pharmacy for the dispensing of the IMPs. However, this delegation must be documented.

Reconciliation between the amounts of IMPs supplied, dispensed and unused must be performed by the CRA / monitor / designee and any discrepancies in the reconciliation of the IMPs should have necessary clarification.

# 8.3 Handling of Unused Investigational Medicinal Products

IMPs that have not been dispensed to the patient will be retained in their original containers by the Investigator under controlled temperature unless otherwise advise by the IMPs that are dispensed but un-dosed (e.g., due to the patient being unwell or withdrawal from study etc.) including unused IMPs returned by the patients will be labeled as "Not For Use", and should be retained at site along with the unused samples. This product will be maintained, under controlled temperature conditions, on site until further instruction is obtained from the

### 8.4 Maintenance of Randomization Code and Dispensing Record

Randomization code and IMP dispensing record will be kept under controlled access. Personnel involved in dispensing of IMPs (dispensing pharmacist), and the Investigator will be accountable for ensuring the compliance to randomization schedule and the monitor will confirm compliance during the monitoring visit.

Note: Details of IMP handling, dispensing, preparation and administration will be as per the latest version of IMP Plan.

Confidential Page 48 of 91

# 8.5 Retention samples

Investigator site shall retain the reserve samples as provided by These samples must be stored in sealed original container under conditions described in section 8.1.1 to preserve the original characteristics of the products for at least 5 years after obtaining the marketing approval or for 5 years after completion of the trial, if not approved for marketing.

Respective clinical site should be responsible for the use of IMPs for conduct of the study and for retention of reserve samples. Site will randomly select the samples from the supplied IMPs for retention as reserve samples in a sealed original container and use the remaining IMPs for study purpose. Each clinical site will be responsible for the appropriate storage of IMPs and to maintain temperature records for the entire duration, until the retention quantities are handed-over to the regulatory agency or until expiration of the 5 year retention period and sponsor's confirmation.

If the investigator is unable to retain the reserve samples at site, a third party may be used for retention of reserve samples after completion of the study.

Retention of IMPs will be as per the applicable regulatory requirements, details of which will be provided in the IMP plan.

Note: Separate study-specific IMP plan will be prepared. The storage, receipt, handling, dispensing and retention of IMPs will be handled as per latest version of the IMP plan.

# 8.6 IMP Non-Conformances

#### 1. Definitions

Non-conformances to the investigational medicinal product (test and reference product) or medical device can include:

- 1) Complaints connected to the quality of the product such as
  - o any fault of quality and/or effectiveness e.g. change of visual appearance, change of amount, damaged tablets/capsules, presence of foreign matter.
  - any fault of the containers and outer packages e.g. surface imperfection, container leakage, broken syringe/plunger, missing contents, device malfunction.
  - o any fault of the labeling e.g. missing or illegible label.
  - any falsification of the medicinal product or medical device e.g. suspected product mix-up, tampering or counterfeiting.
- 2) Deviations connected to the transport of the product, such as damaged transport carton and/or damaged secondary package upon receipt of the shipment, missing drugs from the shipment package, unsuitable transport conditions.

Confidential Page 49 of 91

#### 2. Process

In case any of the non-conformances listed above are detected or information about these nonconformances has been received, the completed Non-conformance Report must be sent to the sponsor study manager within 24 hours. In parallel local monitor or CRA of the respective study must be informed about the non-conformance. If possible, a photo of affected material should be attached to the report. Affected material should be retained and stored according to the storage conditions label and/or returned to sponsor if requested by the sponsor.

### 9.0 SELECTION AND WITHDRAWAL OF PATIENTS

All patients will undergo screening procedure up to 40 days prior to Day 1 (up to 30 days prior to Day 1 for patients that are already receiving a stable dose of Lynparza® (olaparib) tablets). The patients will be selected based on the following inclusion and exclusion criteria.

#### 9.1 Inclusion Criteria

To be eligible for the study, patients must meet all the following inclusion criteria:

First-Line Maintenance Treatment of BRCA-mutated Advanced Ovarian Cancer maintenance
treatment of adult patients with deleterious or suspected deleterious germline or somatic BRCAmutated advanced epithelial ovarian, fallopian tube or primary peritoneal cancer who are in complete
or partial response to first-line platinum-based chemotherapy. Select patients based on a diagnostic
test for BRCA mutation by NGS – Next Generation Sequencing method.

OR

Maintenance Treatment of Recurrent Ovarian Cancer maintenance treatment of adult patients with recurrent epithelial ovarian, fallopian tube or primary peritoneal cancer, who are in complete or partial response to platinum-based chemotherapy.

OR

Advanced Germline BRCA-mutated Ovarian Cancer After 3 or More Lines of Chemotherapy treatment of adult patients with deleterious or suspected deleterious germline BRCA-mutated (gBRCAm) advanced ovarian cancer who have been treated with three or more prior lines of chemotherapy. Select patients based on a diagnostic test for BRCA mutation by NGS – Next Generation Sequencing method.

OR

Germline BRCA-mutated HER2-negative Metastatic Breast Cancer treatment of adult patients with deleterious or suspected deleterious gBRCAm, HER2-negative metastatic breast cancer, who have been treated with chemotherapy in the neoadjuvant, adjuvant, or metastatic setting. Patients with hormone receptor (HR)-positive breast cancer should have been treated with a prior endocrine therapy

Confidential Page 50 of 91

- or be considered inappropriate for endocrine therapy. Select patients based on a diagnostic test for BRCA mutation by NGS Next Generation Sequencing method.
- Non-smoking, non-pregnant, non-lactating female patient ≥18 years of age with a body mass index (BMI) in the range of 18.50 to 30.00 kg/m² (both inclusive).
- Able to give written informed consent for participation in the trial and willing to adhere to protocol requirements.
- 4. Patients that are already receiving a stable dose of Lynparza® (olaparib) tablets (2\*150 mg tablets) 300 mg twice daily for at least 10 days.

OR

Patients requiring Olaparib in the dose of 300 mg (2\*150 mg tablets) twice daily as per the discretion of the Investigators; these patients will be stabilized on Olaparib as a part of study and those patients that tolerate Olaparib in the dose of 300mg twice daily will be randomized in the study. Patients that do not tolerate the mentioned dose or require dose modifications for any reason will be considered as screen failure. Patients who miss 2 or more consecutive doses or more than 3 non-consecutive doses in the Dose Stabilization period will be considered screen failure.

- 5. Patient having an estimated survival of at least 3 months.
- 6. Adequate organ and bone marrow function based upon the following laboratory criteria at the time of eligibility assessment prior to dosing in period 1:

Body system	Parameters
Bone marrow function	a) Hemoglobin≥9.0 g/dL
	b) Absolute neutrophil count ≥1500/uL
	c) Platelet count ≥100,000/uL
	d) WBC count > 3000/mm 
Renal function	Creatinine Clearance > 50 mL/min (calculated based on Cockcroft-Gault formula)

- 7. Eastern Cooperative Oncology Group (ECOG) performance status of 0-2.
- 8. Absence of blood transfusion in the 28 days prior to randomization.
- 9. Women of non child bearing potential with documented evidence of hysterectomy / bilateral salpingectomy / bilateral oophorectomy at least 6 months prior to IMP administration) or postmenopausal for at least 12 consecutive months.

OR

Confidential Page 51 of 91

Women of child bearing potential must have negative pregnancy test at screening visit and before randomization and must agree to use an effective method of avoiding pregnancy (including oral, transdermal or implanted contraceptives [any hormonal method in conjunction with a secondary method], intrauterine device, female condom with spermicide, diaphragm with spermicide, absolute sexual abstinence, use of condom with spermicide by sexual partner or sterile [at least 6 months prior to IMP administration] sexual partner) for at least 4 weeks prior to IMP administration, during the study and up to 6 months after the last dose of IMP. Cessation of birth control after this point should be discussed with a responsible physician.

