## Vital signs and body measurements:

- > Body height: Screening visit
- > Body weight: Screening, End of Study
- > Body temperature, Blood pressure, Heart rate and Respiratory rate:
  - Screening
  - o Day 0, Day 5 and Day 13
  - o Before morning dose on Day 1, Day 6 to Day 9 and on Day 14 to Day 16
  - o At 3 hour after morning dose on Day 6 to Day 9 and on Day 14 to Day 16
  - o End of study (Day 16)
  - o Safety follow up (On day 24±2)
  - Note: Blood pressure, pulse rate, respiratory rate and body temperature prior to IMP administration will be measured within 60 minutes prior to dosing and after administration of the IMP will be measured within ± 30 minutes of the scheduled time.

Additional vital examinations may be performed at any time during the study as per Investigator's judgment; all results must be documented appropriately.

HIV, HCV, HbSAg, and VDRL or RPR (for syphilis): Screening

12-Lead ECG: Screening, Day 5, Day 13 and End of Study (Day 16)

2D-ECHO: Screening

Urine drug Screen (benzodiazepines, opioids, amphetamines, cannabinoids, cocaine and barbiturates) and Alcohol Breath Test: Day 0, Day 5 and Day 13.

Note: Separate mouthpiece will be used in breath test for every patient in the study.

Pregnancy test: Screening visit (Serum), Day 0, Day 5, Day 13 (Urine), and at End of Study Visit (Serum) for FCBP only.

X-ray (chest): To be performed based on Investigator's discretion.

Confidential Page 21 of 91

Hematology, Blood chemistry and Urinalysis: Screening, and at the end of the study (Day 16)

CBC, Creatinine Clearance, S Bilirubin, SGPT and SGOT: Prior to dosing in period 1 (Day -2 to 0) and period 2 (can be performed after evening dose on Day 8) (can be done at local laboratory)

In addition to protocol-specific laboratory tests and/or clinical examinations at scheduled time points, additional tests/clinical examination may be conducted to evaluate patient safety at any time during the study, at the discretion of the Investigator (can be done in local laboratory or nearby clinic/hospital/institution).

Note: It is recommended that general precautions should be taken by the staff with respect to ongoing COVID-19 pandemic situation during the trial.

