#### 10.2 Dosing

### Stabilization Phase:

The patients found eligible for participation in the study, but not yet on a stable dose of Lynparza® (olaparib) tablets, will be enrolled in the Dose Stabilization period. Dose Stabilization period will be applicable for patients that are not on a stable dose of Lynparza® (olaparib) tablets 2\*150 mg (for at least 10 days). Following this, patients will be randomized to participate in the study. Patients that do not tolerate the mentioned dose or require dose modifications for any reason will be considered as screen failure. Patients who miss 2 or more consecutive doses or more than 3 non-consecutive doses in the Dose Stabilization period will be considered screen failure.

Patients that are already on a stable dose of Lynparza® (olaparib) tablets (2\*150 mg twice daily) for at least 10 days and have met the eligibility criteria will be directly randomized for participation in the study.

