# In period I:

On day 0, patient will be asked to reach the site at least 12 hours prior to scheduled dosing on Day 1 and will be housed for 12 hours after morning dose of Day 1. Patient will be administered two tablets (2\*150 mg

Confidential Page 55 of 91

tablets) of investigational medicinal product in morning and evening as per randomization schedule under supervision of trained study personnel at clinical facility.

Dosing on Day 1 (morning as well as evening) would be done at site. Patients will be discharged after administration of evening dose of Day 1 at site. Dosing from Day 2 to Day 5 can be done at home by patients. The patient will be provided with sufficient Investigational medicinal product for dosing at their home for Day 2 and Day 4 (for morning and evening daily dosing at 12-hours interval) and Day 5 morning dosing). Day 5 evening dose will be done at site.

Patient will also be provided with a patient diary card to enter the details of study drug consumption and details of AE (if any) at their home. Patient and their attendant will be provided with adequate instructions to complete the patient diary card at their home.

Patient will be requested to come to the clinical facility for evening dose on Day 5 (at least 12 hours prior to scheduled morning dosing on Day 6) for housing in the clinical facility.

During the patients stay in the clinical facility on Day 6, Day 7 and Day 8, patients will be administered the investigational medicinal product at the scheduled time of dosing in morning and evening daily at 12-hours interval under supervision of trained study personnel.

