## 12.0 CLINICAL AND SAFETY ASSESSMENT

It is the responsibility of the PI to ensure that adequate medical supervision and care is available for the study patients during housing and during the study duration to ensure the utmost safety and well-being of the study patients. At study sites, medical personnel will be available 24 hours a day and physician in charge will remain at the clinical site for at least the first 4 hours following drug administration. On PK sampling days (Day 8 and 16), Investigator will remain at the clinical site for at least the first 4 hours following morning drug administration. In addition, if necessary, Investigators will be available on-call at all times.

Confidential Page 60 of 91

Medical and Medication history and Review of Inclusion and Exclusion Criteria: Screening and at the time of randomization.

HER2 Testing (Only applicable for breast cancer patients): Screening (If the report is not available with the patients at the time of screening).

Germline or Somatic BRCA1 and BRCA2 diagnostic test for olaparib by NGS – Next Generation Sequencing method: Screening (the details for applicable patients and type of sample as per the section 5.6).

Note: The Germline or Somatic BRCA1 and BRCA2 test need not be repeated in those patients who have been started on olaparib post BRCA testing done by NGS – Next Generation Sequencing method.

**Physical examination:** Screening, Day 0, Day 5 and Day 13 and End of Study (Day 16), Safety follow up (on day 24±2).

Demographics: Age, gender, ethnicity and race will be noted at screening visit.

Additional vital examinations may be performed at any time during the study as per Investigator's judgement; all results must be documented appropriately.

HIV, HCV, HbSAg, and VDRL or RPR (for syphilis): Screening

Confidential Page 61 of 91

12-Lead ECG: Screening, Day 5, Day 13 and End of Study (Day 16)

**2D-ECHO**: Screening

Urine drug Screen (benzodiazepines, opioids, amphetamines, cannabinoids, cocaine and barbiturates) and Alcohol Breath Test: Day 0, Day 5 and Day 13

Note: Separate mouthpiece will be used in breath test for every patient in the study

Pregnancy test: Screening visit (Serum), Day 0, Day 5, Day 13 (Urine), and at End of Study visit (Serum) for FCBP only.

X-ray (chest): To be performed based on Investigator's discretion.

Hematology, Blood chemistry and Urinalysis: Screening, and at the end of the study (Day 16).

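### The second pregnancy test is tied to randomization and Day 0, so a woman who starts olaparib in Dose Stabilization can do so on a screening result up to 30 days old (low severity; check Annexure I first)

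*Protocol*

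**What the plan says.** Protocol 9.1, inclusion 9, sets the eligibility rule: "Women of child bearing potential must have negative pregnancy test at screening visit and before randomization". The synopsis and SAP 6.1 repeat it.

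Protocol section 12.0 gives the schedule of pregnancy tests: "Screening visit (Serum), Day 0, Day 5, Day 13 (Urine), and at End of Study visit (Serum) for FCBP only". The synopsis list is the same.

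Protocol 10.2 (Stabilization Phase) covers patients who are not yet on a stable olaparib dose. They first take marketed olaparib inside the study. Then: "Following this, patients will be randomized to participate in the study". Patients who miss two or more doses in a row fail screening, and so do those who miss "more than 3 non-consecutive doses in the Dose Stabilization period will be considered screen failure".

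On timing, Protocol 9.0 says: "All patients will undergo screening procedure up to 40 days prior to Day 1". Protocol 7.4 shows that the stabilization days fall inside that window: "Screening period including 10-day Dose Stabilization period: 40 days".

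Protocol 5.9 requires a pregnancy test before olaparib is started and gives no maximum interval. Inclusion 9 requires contraception for at least 4 weeks before the investigational product, during the study, and for 6 months after the last dose.

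**The concern.** The plan places its second pregnancy test by reference to randomization. That suits patients who arrive already on olaparib. It does not suit those who start olaparib in the study, because their first exposure comes about ten days before randomization. For them, the Day 0 test falls at the end of the stabilization course.

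The hazard is one that the protocol itself describes. Section 5.4 reports malformations and embryo-fetal toxicity in rats at exposures lower than those reached in patients on 300 mg twice daily, which is the stabilization dose. If contraception fails after an early screening test, no test listed in these sections would show it before dosing begins.

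A long interval is plausible. Section 10.2 puts patients into stabilization once they have been found eligible. Section 12.0 makes BRCA sequencing a screening procedure and waives a repeat only for patients who started olaparib after such a test. A woman new to olaparib in one of the BRCA-selected indications may therefore wait for a result. The documents give no turnaround time. Recurrent ovarian cancer needs no biomarker test (section 5.6).

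**Working it through.** **Inputs**

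- Screening window: up to 40 days before Day 1 (Protocol 9.0).
- Dose Stabilization: 10 days, inside the 40 (Protocol 7.4), at two doses a day.
- Tests before Day 1: screening and Day 0 (Protocol 12.0 and synopsis).
- Permitted missed stabilization doses: up to 3, not consecutive (Protocol 10.2).
- Contraception lead-in: 4 weeks, or 28 days, before the investigational product (inclusion 9). Protocol 8.2 gives that product only to randomized patients, so the lead-in is counted back from Day 1.

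**The plan's own figure.** With 40 days of screening, 16 of treatment and 8 to follow-up, the total is 40 + 16 + 8 = 64 days. For patients already stable it is 30 + 16 + 8 = 54 days. Both match section 7.4, which confirms that the 10 stabilization days sit inside the 40.

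**Age of the screening result at the first stabilization dose.** Age = (days from screening to Day 1) − 10.

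| Screening, days before Day 1 | Age of result at first dose, days |
|---|---|
| 10 | 0 |
| 20 | 10 |
| 30 | 20 |
| 40 | 30 |

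Day labels give the same maximum. The protocol has a Day 0, so 40 days before Day 1 is Day −39. Ten dosing days ending on Day 0 start on Day −9. From Day −39 to Day −9 is 30 days.

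**Doses taken before the Day 0 test.** Scheduled doses are 10 × 2 = 20. On check-in, section 10.2 says: "On day 0, patient will be asked to reach the site at least 12 hours prior to scheduled dosing on Day 1". A test done around check-in may therefore fall just before or just after the Day 0 evening dose.

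- After the evening dose: 20 scheduled, or 20 − 3 = 17 with three permitted misses.
- Before the evening dose: 19 scheduled, or 19 − 3 = 16 with three permitted misses.

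The range is about 16 to 20 doses.

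**Interval between listed tests.** From Day −39 to Day 0 is up to 39 days, and first exposure falls within it. Later tests on Days 0, 5, 13 and 16 are 5, 8 and 3 days apart.

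**Contraception lead-in.** Counted back from Day 1, the express 4-week period begins 28 − 10 = 18 days before the first stabilization dose.

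**Effect of a short window.** With an assumed 3-day limit, the maximum age falls from 30 days to 3, a reduction of 27 days.

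**The case against.** The strongest objection is that the Schedule of Events, Annexure I, is not in the text available here. Both errata correct entries in it, so it is a working schedule and could list a test at the start of stabilization. This stands, and it makes checking the annexure the first step. It does not dispose of the point: the lists in section 12.0 and the synopsis read as complete, inclusion 9 is the operative eligibility rule, and the legible errata add no pregnancy test.

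Second, no rule in the documents is broken. A reader might infer that section 5.9 is breached, or that olaparib can be started with no pregnancy test at all. Neither is supported. A serum test at screening is mandatory and comes before any study olaparib, and section 5.9 sets no interval. The 3-day window is an example of this review's own, so the change is a tightening and not the correction of an error.

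Third, other safeguards exist. Inclusion 2 and exclusion 14 bar pregnant women, withdrawal criterion 9 covers a patient who becomes pregnant, and section 12.0 lets the investigator order extra tests. A reader might also infer that stabilization falls outside the contraception rule. It does not: four weeks before Day 1 covers all ten stabilization days and about 18 days before them, and contraception is also required during the study. These safeguards lower the risk. None of them schedules a test before first exposure.

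Fourth, the harm is not quantified. That is fair. The documents do not say how many women of child-bearing potential will enter through stabilization, so no count of affected women or expected pregnancies can be derived from them.

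**Conclusion.** The point holds as a low-severity safety improvement. Read as written, inclusion 9, section 12.0, the synopsis and SAP 6.1 let a woman take her first olaparib dose in the study on a pregnancy result 0 to 30 days old. The next listed test comes after about 16 to 20 doses.

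The 30-day maximum assumes screening at the start of the 40-day window and a stabilization course of exactly ten days ending on Day 0; counting conventions could move it by a day. The gap concerns only women of child-bearing potential who start olaparib in the study. Those already on a stable dose were exposed before entry.

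A test near the first dose would detect pregnancies that began after an old screening result and have become detectable. It would not detect very recent conceptions. The documents do not show that the full plan lacks such a test, because Annexure I has not been seen.

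**What to change.** Check Annexure I first. If it already lists a test before the first stabilization dose, bring Protocol 9.1, section 12.0, the synopsis and SAP 6.1 into line with it and change nothing else.

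If it does not, add to inclusion 9, after the requirement for a test before randomization: *and, for patients entering Dose Stabilization, within 3 days before the first dose of olaparib in that period; a screening test done inside this window counts*. The sponsor may choose another short window. Make the same change to inclusion 9 in the synopsis and SAP 6.1. Add the time point, with a urine test acceptable, to the pregnancy test lists in section 12.0 and the synopsis and to Annexure I. Keep the Day 0 test and the contraception wording as they are.

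The cost is at most one extra urine test per affected woman, and none where the screening test falls inside the window. A urine test adds nothing to the 187 mL blood limit in section 10.6. A few women may wait briefly for a result before their first dose. The wording changes in several places and adds an eligibility condition. Erratum 02 has already changed the timing of safety laboratory tests, so an erratum may be enough. If the sponsor judges the change significant, section 16.1 requires an amendment with Ethics Committee approval.
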